After careful consideration of potential etiologies of CI that could be safely attenuated, and of multiple pharmaceutical and non-pharmaceutical agents that are both safe and biologically plausible to be effective against CI, our team has identified lactoferrin as an important potential treatment for CI and related declines in functional consequences in older adults. Lactoferrin is a basic glycoprotein found in most exocrine secretions and in neutrophil granules that has a pleiotropic impact on innate immune system activation (8-10). It binds to invading organisms and bacterial cellular wall products rendering them less immunogenic and easier to degrade, modulates the adaptive immune system, and it directly suppresses inflammation via NfKB mechanisms, especially in the GI tract (9-15). A prior study of oral bovine lactoferrin administration in post-menopausal women demonstrated significant reductions of CRP and IL-6 level (16). Given this background, we hypothesize that oral lactoferrin will attenuate inflammatory signaling in adults with CI. We further hypothesize that the lactoferrin induced CI attenuation will attenuate decline or facilitate measureable improvement in specific functional and cognitive measures in older adults.

To test these hypothesizes, a randomized, placebo controlled pilot trial of rhlactoferrin (rhLF) in adults over age 70 is proposed that aims to assess the efficacy of this potent anti-inflammatory nutrient on CI and restricted mobility. This study will enroll 60 patients (30 randomized to rhlactoferrin (rhLF) and 30 randomized to placebo).

At the conclusion of this pilot study, we will have determined whether recombinant human lactoferrin (rhLF) can safely reduce measures of CI in older adults, and if it has the potential to meaningfully influence important measures of physical and cognitive function known to be influenced by CI. This information will in turn be utilized to develop a more definitive clinical trial of rhlactoferrin (rhLF) for CI and adverse health outcomes in older adults.

[figure not shown]
2. Objectives

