Measurements Performed at Visits:

Phlebotomy (primary outcome measure): Primary outcome will be serum IL-6 and sTNFR1 as measured by ELISA as previously performed in the PI's laboratory by an experienced laboratory technician. Blood will also be measured for CBC w/Diff, and CMP, these measures will be made from blood drawn at SV, ABT, BV, FU1, FU3 and FU6. Rationale for the choice of these measures are provided above in the background section.

A Physical Exam will be taken at SV. A Medical History will be taken at SV and a Brief Medical History Review at BV and all subsequent FUV. These are to assess eligibility or contraindicate the intervention, detect new conditions or complications and other safety signals, and to measure important covariates (i.e. demographics, past medical history, current activity levels, routine medication, and vitamin use).

4 meter walk: Speed of walking at usual pace over 4 meters will be measured at the SV, BV, FU3, and FU6.

Six-minute walk: This is performed at the BV, FU3, and FU6 by having the participant walk along a straight hallway for six minutes and measuring the distance walked and the sensation of leg fatigue and dyspnea. The participant is given scripted prompts at one-minute intervals, but the test is largely self-directed and self-limited.

Short Physical Performance Battery (SPPB): This is an assessment of lower extremity functioning comprised of gait speed, balance, and leg strength and is performed at the BV and FU6. As part of the SPPB, participants will complete a balance test assessing their ability to stand without assistance and a chair stand test.

Cognitive Function Measures: The Digit Symbol Substitution Test (DSST) is a sensitive measure in cognitively normal older adults. It measures attentional control and switching, and more broadly executive processes and thus is not sensitive to impairment in particular brain regions. It is a highly precise measure across the range from cognitively normal to mildly impaired older adults and takes about 90 seconds to administer (75). The DSST will be conducted at BV, FU3, and FU6. The Trail Making A and B Test measures executive functioning and task-switching, is highly sensitive to change and takes 5-10 minutes to administer (76). This test will be performed at BV, FU3, and FU6. An MMSE (a mini-mental state exam) will also be performed at the BV.

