Based on a two-sided two-sample t-test with a Type I error of 0.05, a sample size of 23 subjects per group (46 in total) will achieve 80% power to detect a difference of 0.86 SD or greater in logIL-6 between the treatment group and the placebo group at the end of the 6-month trial. Secondly, we will compare the linear rate of change in logIL-6 between the treatment and the placebo groups by modeling the individual trajectories of the outcome. With 20 subjects per group, three repeated measurements of IL-6 assessed at baseline, 3, and 6 months, and a correlation of 0.54 between measurements, we will have 80% power to detect a difference of 1.3 SD units (equivalent to a cross-sectional between-group difference of 0.65SD different at 6 months) or greater in the yearly rate of change in logIL-6 between the treatment and the placebo group. The within subject between-measurement correlation of 0.54 was estimated using longitudinal data from the Women's Health and Aging Study II. Therefore, using longitudinal data, we will have adequate power to detect a difference similar to the 0.63 SD (or 2.5 pg/mL) difference observed at the end of a 6-month, randomized clinical study of a ribonuclease-enriched lactoferrin supplement in post-menopausal women (16). Given these calculations, we are aiming to recruit up to 60 individuals, 30 in each group, in order to maximize our ability to detect differences between treatment and placebo groups. This increased number beyond what are calculated here will take into account anticipated drop outs during the treatment period and leave us with an estimated 'complete completer' group of 46 total. In addition, we are estimating that we will need to have at least 250 individuals recruited into the protocol in order to identify those eligible by inflammatory mediator criteria listed above.

8. Risks

Six Minute Walk Test: This is performed by having the participant walk along a straight hallway for six minutes and measuring the distance walked and the sensation of leg fatigue and dyspnea. The participant may stop at any time if they feel uncomfortable. As with any exercise test, there is a theoretical risk that a participant could suffer cardiac risk from arrhythmia or ischemia, or orthopedic risk from falling or stumbling. Risks are minimized by conducting the test in a medically supervised environment with trained personnel.

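### The month-6 logIL-6 comparison is powered with an unadjusted t-test on an expected 46 completers of 60, with no all-randomised rule or missing-data method; baseline adjustment and a longitudinal model would serve it better

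*Combined protocol and SAP*

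**What the plan says.** The only statistical text is Section 7, Study Statistics. It opens with the month-6 comparison of logIL-6, a t-test between the arms at the two-sided 5% level, for which "a sample size of 23 subjects per group (46 in total) will achieve 80% power". The target is a between-arm difference of 0.86 SD, assessed "at the end of the 6-month trial".

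A second analysis compares the linear rate of change in logIL-6 by modelling individual courses. It is powered on 20 per group with IL-6 at baseline, 3 and 6 months and a within-person correlation of 0.54. Section 7 relies on this longitudinal comparison for adequate power near the 0.63 SD seen in an earlier 6-month trial of a lactoferrin supplement.

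On numbers, "we are aiming to recruit up to 60 individuals, 30 in each group"; the excess over the calculated size is there to absorb dropout during the treatment period and "leave us with an estimated 'complete completer' group of 46 total". The Abstract agrees: "This study will enroll 60 patients (30 randomized to rhlactoferrin (rhLF) and 30 randomized to placebo".

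On blood sampling, Section 4 (Measurements Performed at Visits, Phlebotomy) names IL-6 and sTNFR1 as the primary outcome, then adds CBC and CMP, and then says "these measures will be made from blood drawn at SV, ABT, BV, FU1, FU3 and FU6".

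The document defines no analysis population. It contains no statement that all randomised participants are analysed in their assigned arm, no missing-data method and no sensitivity analysis.

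**The concern.** A two-sample t-test at month 6 discards anyone without a month-6 sample and makes no use of the baseline value, although baseline blood is drawn from everyone. The plan itself expects about 23% to be lost and does not say how that loss is handled.

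Two things are at stake. The first is efficiency: with a baseline correlation of 0.54, an unadjusted comparison wastes information already in hand. The second is protection of the randomised comparison. Participants are 70 or older, are selected for raised inflammatory markers and take twelve capsules a day (Section 6). Tolerability and adherence are study objectives, so they are not taken as settled. If those who leave differ in IL-6, and differ more in one arm than the other, a comparison of those who remain is no longer the randomised one. The result is meant to inform a larger trial, so a distorted estimate would carry forward.

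**Working it through.** **Inputs from the documents.** Two-sided alpha 0.05; 23 per group; 0.86 SD; 60 randomised 1:1; 46 expected completers; correlation 0.54; 0.63 SD as the effect seen in the earlier trial (all Section 7). Effects are in SD units of logIL-6, so SD = 1.

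**Assumptions, not in the documents.** Equal correlation of 0.54 between all visits; 7 lost per arm; in the simulations, half of the losses before FU3 and half after. The dropout mechanisms are stated below.

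**1. The plan's own figure.** Noncentral-t power for 23 per group at 0.86 SD is 81.4%, and 23 is the smallest n per group reaching 80%. The figure reproduces.

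**2. Implied loss.** (60 − 46)/60 = 14/60 = 23.3%. Section 7 states no rate.

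**3. Precision at month 6.**
- Unadjusted t-test, 23 per arm: SE = √(2/23) = 0.295.
- Unadjusted t-test, 30 per arm: SE = √(2/30) = 0.258. The ratio is √(30/23) = 1.14, so the SE is 14% larger with completers only.
- Baseline-adjusted, same 23 per arm: SE = √(2(1 − 0.54²)/23) = √(2 × 0.7084/23) = 0.248, a reduction of about 16% from 0.295.
- Longitudinal model with a common baseline mean, adding the 7 per arm who leave: SE = 0.245 if they give data to month 1, 0.243 if to month 3. That is a further 1–2%.

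**4. Power at 0.63 SD with purely random dropout.** The t-test figure agrees with the noncentral-t calculation (55.2%); the other two are simulated.

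| Analysis | Participants | Power |
|---|---|---|
| Unadjusted t-test | completers | about 55% |
| Baseline-adjusted (ANCOVA) | same completers | about 69–70% |
| Longitudinal model | all randomised | about 71–72% |

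Most of the gain comes from using baseline; partial data from those who leave add only a few points. The simulated longitudinal model treats the covariance as known, which flatters it slightly.

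**5. Bias, simple arithmetic.** If the 7 of 30 missing in one arm differ from that arm's completers by k SD, and missingness in the other arm is uninformative, the completer difference is off by (7/30)k: 0.06, 0.12 and 0.23 SD for k = 0.25, 0.5 and 1.0.

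**6. Bias, simulated** (30 per arm, about 23–25% dropout, 1,500 to 4,000 trials per scenario). Log odds of 1.0 and 1.5 per SD are odds ratios of e^1.0 = 2.7 and e^1.5 = 4.5.
- *Active-arm dropout depends on FU1 IL-6, placebo dropout random, no true effect.* The t-test is off by about 0.10–0.17 SD in favour of rhLF, with Type I error about 7–8%. Completer ANCOVA is off by about 0.05–0.06 SD. The longitudinal model using FU1 is within about 0.01 SD.
- *Same mechanism, true effect 0.63 SD.* The t-test estimates about 0.75–0.80 SD; the longitudinal model about 0.63–0.64 SD.
- *Same relation to IL-6 in both arms, no true effect.* t-test bias is about 0.00.
- *Same active-arm mechanism, FU1 IL-6 not available.* Longitudinal-model bias is about 0.04–0.07 SD (about 0.06 at odds ratio 4.5).
- *Active-arm dropout depends on the unobserved month-6 value.* The longitudinal model is off by about 0.12–0.15 SD; the t-test by about 0.21–0.25 SD.

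**The case against.** A reader might infer that the plan restricts the efficacy analysis to completers and drops 14 participants. The documents do not say that. The sentence about 46 is a sample-size allowance, and the t-test appears only as the basis of the power calculation. The dropout it refers to is during the treatment period, about 87 days (Section 6), and someone who stops capsules could still give month-6 blood. This objection stands. What remains is that the test as stated cannot use a participant without a month-6 value, and no other text offsets this.

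Section 7 also plans a trajectory analysis, which could include people with partial data. That stands too, but the text does not say that it will include them.

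A reader might also infer that dropout itself wrecks the power. It does not: recruitment of 60 already budgets for it, and 80% power at 0.86 SD is kept. The shortfall at 0.63 SD comes mainly from ignoring baseline.

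The bias scenario is one-sided by construction. No figure in the documents supports strong IL-6-related dropout on rhLF alone, both arms take matching capsules, and Section 6 reports minimal or no side effects in the earlier bovine lactoferrin study. This stands, so the bias is a conditional risk and not a prediction.

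Finally, it is unclear whether IL-6 is assayed at FU1. The list of draws in Section 4 directly follows the mention of CBC and CMP, and Section 7 counts only three IL-6 measurements. The near-zero bias of the longitudinal model depends on that value.

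**Conclusion.** The point holds in limited form. The stated month-6 test is unadjusted and usable only with a month-6 value, about 23.3% loss is implied, and no analysis population or missing-data method is given.

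- **Power.** The plan's own target is met. At 0.63 SD, about 55% could become about 71–72%, of which about 69–70% is reached by baseline adjustment alone. This rests on the 0.54 correlation holding between all visits.
- **Bias.** About 0.10–0.17 SD if dropout relates to IL-6 in the active arm only, at assumed odds ratios of 2.7–4.5 per SD; essentially none if the relation is the same in both arms. The documents fix neither its direction nor its size, so they do not support saying that the planned test will exaggerate the effect.
- **Limits of the remedy.** A longitudinal model removes this bias only when dropout depends on observed values. It leaves about 0.06 SD without FU1 IL-6 (at odds ratio 4.5), and more if dropout depends on unobserved values.

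This should be changed, because a better analysis is available at little cost. It does not invalidate the design.

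**What to change.** In Section 7:

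- State that the primary analysis includes all randomised participants in their assigned arm.
- Make that analysis a longitudinal model of logIL-6 with visit, arm-by-visit and a common baseline mean, using BV, FU3 and FU6, and FU1 if IL-6 is assayed at that scheduled draw. Estimate the arm difference at the named primary visit.
- Say explicitly whether IL-6 is measured at FU1, so that Sections 4 and 7 agree.
- Continue the scheduled blood draws in participants who stop capsules but remain in the study.
- Report the completer t-test as a sensitivity analysis.

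The cost is statistics-section wording and slightly more analysis work. If FU1 IL-6 is not already planned, there is also one additional assay on blood that is drawn anyway. No extra visit or draw is needed.
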